4.4.2 Secondary endpoints post-op

Post-op will be measured at 5-10 min before CBP (T0), 5-10 min after CBP (T1), 2h after weaning from CPB (T2), 6h after weaning from CPB (T3), 8-12 hours post CBP-weaning, 24h after weaning from CPB (T4), 4 days after weaning from CPB (T5) (all variables are not

STATISTISKA KONSULTGRUPPEN		Statistical Analysis Plan	
Protocol: The prophylactic effect of Levosimendan in reducing acute kidney injury postoperatively in pediatric patients undergoing corrective heart surgery	Protocol No: MiLe-1	Version: 1.0	Page 11 of 17

present at all timepoints). Changes from T0 will be calculated for all variables where applicable.

Hemodynamic parameters measured at T0-T4 (not T5) and additionally at 8-12 hours post CPB-weaning

- Heart rate (BPM)
- Heart rhythm (SR/NR/Other)
- Pacing (Yes/No) (Missing on T0)
- Mean BP M A P (mmHg)
- CVP (mmHg)
- Central venous saturation (%)
- NIRS brain (%)
- NIRS kidney (%)
- Ventilated (Yes/No)

Arterial blood gas test

- pH
- sO₂ (%)
- cLac (mmol/L)
- Hb (g/L)
- Hct

Rate of vasoactive drugs

- Inotropic score
- 2 ml blood sample in ice taken (YES/NO)

NGAL

- NGAL plasma

T5

- T5 taken at postoperative day nr (2-7)

4.4.3 Secondary endpoints Follow up postop days 1-4

Fluid balance

- Fluid balance ((ml)
- Urine (ml)
- Weight (g)
- %FO (fluid balance (ml)/1000_(+24 hours) /preop weight (kg)) x 100. For example for day 1 the Fluid balance measured at day 2 will be used. If a negative fluid balance set %FO to 0.
- Cumulative %FO (day 1+2, day 1+2+3, day 1+2+3+4)

STATISTISKA KONSULTGRUPPEN		Statistical Analysis Plan	
Protocol: The prophylactic effect of Levosimendan in reducing acute kidney injury postoperatively in pediatric patients undergoing corrective heart surgery		Protocol No: MiLe-1	Version: 1.0 Page 12 of 17

- Peritoneal Dialysis day 1 and day 2 from Status and medication_1 and Status and medication_2

Morning lab results (Postop day 1 is under hemodynamics_1, etc.)

- Hb (g/L)
- Hct
- Leucocytes ($\times 10^9/L$)
- Trombocytes ($\times 10^9/L$)
- C R P (mg/L)
- Albumin (g/L)
- Creatinine ($\mu\text{mol}/L$)
- Corrected creatinine [$(\text{creatinine } (\mu\text{mol}/L) \times [1 + (\text{fluid balance } (L)_{(+24 \text{ hours})} / (\text{weight } (\text{kg}) \times 0.6)])]$ only calculated for day 1-3. For example for day 1 the Fluid balance measured at day 2 will be used. If negative values in fluid balances, fluid balance is set to 0.
- Corrected creatinine (age differentiated), same as above but (in the formula) using 0.75 for infants younger than 5 months and 0.6 for infants/adults older than 5 months.
- AKI_(72 hours) and AKI_(96 hours) in same fashion as in primary endpoint
- AKI stage at 48 (24 and 48), 72 and 96 hours.
 - Stage 0 (no AKI, corrected creatinine up to 1.49 times screening creatinine)
 - Stage 1 (corrected creatinine 1.5-1.99 times screening creatinine)
 - Stage 2 (corrected creatinine 2-2.99 times screening creatinine)
 - Stage 3 (corrected creatinine 3 (or more) times screening creatinine or need of dialysis)
- eGFR Creatinine (calculated value from CRF)
- Cystatin C (mg/L)
- eGFR Cystatin C, calculated using formula $91 \times \text{Cystatin C } (\text{mg/L})^{-1.213}$
- Urea (mmol/L) Use value in database (no recalculation is needed), in CRF the unit stands as $\mu\text{mol}/L$ but it is actually mmol/L.
- Combined eGFR (mL/min per 1,73 m²)
 - $39.1 \times [\text{height } (\text{m})/\text{Serum creatinine } (\text{mg/dl})]^{0.516} \times [1.8/\text{Cystatin C } (\text{mg/L})]^{0.294} \times [30/\text{Urea } (\text{mg/dl})]^{0.169} \times [1.099]^{\text{male}} \times [\text{height } (\text{m})/1.4]^{0.188}$
 - Conversion formula Creatinine (mg/dl) = Creatinine ($\mu\text{mol}/L$)/88.42
 - Conversion formula Urea (mg/dl) = Urea (mmol/L)/0.3571

Morning Hemodynamics (Postop day 1 is under Test results and hemodynamics_1 etc)

- Heart rate (BPM)
- Rythm (Sinus rhythm/Nodal rythm/Other)

STATISTISKA KONSULTGRUPPEN		Statistical Analysis Plan	
Protocol: The prophylactic effect of Levosimendan in reducing acute kidney injury postoperatively in pediatric patients undergoing corrective heart surgery		Protocol No: MiLe-1	Version: 1.0 Page 13 of 17

- Pacing (Yes/No)
- M A P (mmHg)
- Ventilated (Yes/No)

Rate of vasoactive drugs at 06:00 am

Inotropic scoreBlood gas at 6 am (Postop day 1 is under Test results and hemodynamics_1 etc)

- pH
- sO₂ %
- pO₂ (kPa)
- Hb (g/L)
- Hct
- cLac (mmol/L)
- CV saturation (%)

Cardiopulmonary bypass and use of cortisone in OR

- CPB time (minutes) (taken from CRF page "Drugs and treatment; cardiopulmonary bypass")
- Crossclamp time (minutes)
- Lowest temperature CPB (degrees celcius)
- Use of cortisone in OR (Yes/No)

Other parameters

- length of mechanical ventilation postoperatively (hours) (collected outside of CRF, external file)
- RACHS-Score 1 (VSD = 2, Fallot = 2, AVSD = 3) (collected outcome crf page)
- Comprehensive Aristotle Score (collected outcome crf page)
- Length of stay PICU (days) (change Finland subjects by minus 1 day)
- Length of hospital stay (days) (change Finland subjects by minus 1 day)
- Re-operation within 96 hours (Yes/No from Important information) (listing only)
- Re-operation (Yes/No from Important information) (listing only)

Other relevant biomarkers may be analysed at a later occasion and will not be specified here.

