4.2.2 Treatments and medication in ICU

Concomitant medications will be presented per day (Medications in the ICU on the operative day (Status and medication_1), postop day 1 (Status and medication_2), postop day 2 (Status and medication_3), postop day 3 (Status and medication_4), postop day 4 (Status and medication_5)) and postop day 1+2 and at any time.

- Albumin infusion (Yes (>0 ml)/No(0 ml))
- Trombocyte transfusion (Yes (>0 ml)/No(0 ml))
- RBC (Yes (>0 ml)/No(0 ml), RBS in CRF miss spelling)
- Plasma (Yes (>0 ml)/No(0 ml))
- Betablocker (Yes/No)
- Cordarone (Yes/No)
- Furosemide (Yes/No)
- Furosemide (mg)
- Ethacrynic acid (Yes/No)

STATISTISKA KONSULTGRUPPEN		Statistical Analysis Plan	
Protocol: The prophylactic effect of Levosimendan in reducing acute kidney injury postoperatively in pediatric patients undergoing corrective heart surgery		Protocol No: MiLe-1	Version: 1.0 Page 10 of 17

- Ethacrynic acid (mg) (Reomax in CRF)
- hANP (Yes/No)
- Spironolactone (Yes/No)
- Spironolactone (mg)
- Methylprednisolone (Yes/No)
- Hydrocortisone (Yes/No)
- Betametason (Yes/No)
- Cortisone: Methylprednisolone, Hydrocortisone or Betametason (Yes/No)
- NO (Yes/No)
- Other medication (free text)
- Dialysis (Yes/No)
- NSAID (Yes/No, Search text Other specify field, Comments field, Extra comments and Important information:info_other_comments for NSAID, Ibuprofen, Brufen) (listing only)
- Vancomycin (Yes/No, Search text field Other specify field, Comments field, Extra comments and Important information:info_other_comments for Vancomycin, Vancocin) (listing only)
- Use of contrast (Yes/No from Important information) (listing only)
- Study drug in the PICU (Study drug in CRF):
 - Study drug according to protocol (YES/NO),
 - Milrinone started (YES/NO)

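### SAP 4.4.3 reads peritoneal dialysis for days 1 and 2 from the CRF pages that SAP 4.2.2 assigns to the operative day and postoperative day 1, and AKI Stage 3 names no dialysis source

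*SAP*

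**What the plan says.** Four parts of the SAP bear on this.

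- **Page map, section 4.2.2.** ICU treatments are presented by day, with the pages assigned as "Medications in the ICU on the operative day (Status and medication_1), postop day 1 (Status and medication_2), postop day 2 (Status and medication_3", continuing "postop day 3 (Status and medication_4), postop day 4 (Status and medication_5)) and postop day 1+2 and at any time". The list of variables under this map includes "Dialysis (Yes/No".
- **Dialysis line, section 4.4.3.** Under the heading "4.4.3 Secondary endpoints Follow up postop days 1-4", the last item of the fluid-balance block is "Peritoneal Dialysis day 1 and day 2 from Status and medication_1 and Status and medication_2".
- **Laboratory page index, section 4.4.3.** The next block opens with "Morning lab results (Postop day 1 is under hemodynamics_1, etc".
- **AKI staging, in that laboratory block.** The times are "AKI stage at 48 (24 and 48), 72 and 96 hours", and the top grade is "Stage 3 (corrected creatinine 3 (or more) times screening creatinine or need of dialysis". No field, page or day is given for the dialysis criterion.

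The primary endpoint in SAP 4.4.1 rests on corrected creatinine alone. SAP 8.2 plans Figure 14.2, AKI stage over time up to 96 hours.

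**The concern.** The SAP uses two numbering systems for its CRF pages. On the laboratory pages the suffix equals the postoperative day. On the Status and medication pages the suffix runs one ahead of it, because `_1` is the operative day. The dialysis line uses Status and medication pages as though they followed the laboratory numbering.

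Two things are at stake. The first is the dialysis tabulation itself, which would show the wrong days. The second is AKI Stage 3. Dialysis is one of only two routes to that grade, and the SAP does not say which variable supplies it. The only dialysis variable in the section that defines the stages is this two-day line, so a programmer might use it. A dialysed infant whose corrected creatinine stayed below 3 times the screening value could then be placed in Stage 0 to 2. Two analysts following the same SAP could stage the same infant differently.

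**Working it through.** The documents give no dialysis figure to reproduce, so the check compares the sections directly.

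**Step 1: the day that each page represents.** Section 4.2.2 gives: postoperative day = suffix − 1. The dialysis line in 4.4.3 implies: day = suffix. The difference is one day.

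| Status and medication page | Day under SAP 4.2.2 | Label in the 4.4.3 dialysis line |
|---|---|---|
| `_1` | operative day | day 1 |
| `_2` | postoperative day 1 | day 2 |
| `_3` | postoperative day 2 | not read |
| `_4` | postoperative day 3 | not read |
| `_5` | postoperative day 4 | not read |

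So the line returns the operative day and postoperative day 1. Postoperative day 2 drops out because of the page shift. Days 3 and 4 drop out for a different reason: the line covers only two days.

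**Step 2: the days that each staging time needs.** SAP 5.3 ties the primary outcome to creatinine on postoperative days 1 and 2, so 24 and 48 hours correspond to days 1 and 2. I take 72 and 96 hours as days 3 and 4. The table shows which postoperative days would be unread under three possible sources for the Stage 3 criterion. The SAP specifies none of them.

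| Staging time | Postoperative days needed | Unread if source is the line as written (`_1`, `_2`) | Unread if source is the line with pages corrected (`_2`, `_3`) | Unread if source is the daily field |
|---|---|---|---|---|
| 48 h | 1–2 | 2 | none | none |
| 72 h | 1–3 | 2, 3 | 3 | none |
| 96 h | 1–4 | 2, 3, 4 | 3, 4 | none |

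Correcting the pages repairs the 48-hour stage only. The later stages also need a source that extends to days 3 and 4, and the daily field in 4.2.2 already provides one.

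**Step 3: which infants could be misclassified.** Three conditions must hold together: Stage 3 is derived from the two-day line, dialysis was first given after postoperative day 1, and corrected creatinine did not reach 3 times screening. An infant who meets the creatinine criterion is in Stage 3 whatever the dialysis source.

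**The case against.** The strongest counter-argument concerns the link to AKI staging. A reader might infer that dialysis on days 2 to 4 is lost from Stage 3 because of the page error. The documents do not support that. The Stage 3 rule names no source. It speaks of dialysis without qualification, whereas the misnumbered line concerns peritoneal dialysis and sits in a different block. Section 4.2.2 lists a daily yes/no dialysis field from the operative day to day 4; if Stage 3 uses it, none of those days is missed. Even if Stage 3 used only the two-day line, the page shift would account for day 2 alone. This objection stands, and it limits the Stage 3 consequence to something that could happen.

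Two benign readings of the line itself are also possible.

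- **Day 1 as the operation day.** The protocol uses that label in Table 6 (section 8.1). But SAP 4.2.2 separates the operative day from postoperative day 1, and the heading of 4.4.3 counts postoperative days. On this reading the pages would match their labels, yet postoperative days 2 to 4 would still be absent.
- **Pages `_1` and `_2` as the periods before the first two morning samples.** That might serve the 48-hour stage. The SAP does not say so, and the 72- and 96-hour stages would still need later pages.

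It is also fair to object that the same offset should not be assumed for fluid balance. The SAP names no CRF page for fluid balance, so no offset is shown there.

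**Conclusion.** The page assignment in SAP 4.4.3 is wrong as written, on the natural reading that its days are postoperative days. The variable is one day early, labels operative-day dialysis as day 1 and omits postoperative day 2.

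The dialysis criterion for Stage 3 is unspecified. If it were taken from this line, dialysis first given on day 2, or on days 3 to 4, could be missed, for the two separate reasons shown above. Operative-day dialysis could also count towards Stage 3 without the SAP having decided that it should. The net direction of any error therefore cannot be assumed.

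The reach is limited to the dialysis tabulation and secondary AKI staging. The primary 48-hour AKI endpoint is unaffected. The number of infants affected cannot be estimated, because the documents give neither a dialysis rate nor its timing. The point is worth correcting because the discrepancy is plain and the remedy uses data that the CRF already holds.

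**What to change.** In SAP 4.4.3:

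1. Reconcile the dialysis line with the map in 4.2.2, so that postoperative days 1 and 2 are read from Status and medication `_2` and `_3`.
2. State that the Stage 3 dialysis criterion comes from the daily yes/no field in 4.2.2: `_2` and `_3` for 48 hours, adding `_4` for 72 hours and `_5` for 96 hours.
3. State whether operative-day dialysis (`_1`) counts towards staging.
4. State whether any dialysis counts or only peritoneal dialysis.

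Items 3 and 4 are endpoint definitions for the sponsor to settle; the documents do not answer them. They should be settled before database lock and without reference to treatment allocation. The cost is a few lines of SAP text and a corrected variable map, with no new data collection.

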4.5 Safety Variables

4.5.1 Adverse Events

Adverse Event within 28 days from surgery. AEs are collected in the following 5 categories at CRF page Adverse Events:

- Heart rate > 200/min at these time points: 2, 6, 10-12 hours after CPB-weaning, first postop morning at 6 am, 24 hours after CPB-weaning

STATISTISKA KONSULTGRUPPEN		Statistical Analysis Plan	
Protocol: The prophylactic effect of Levosimendan in reducing acute kidney injury postoperatively in pediatric patients undergoing corrective heart surgery	Protocol No: MiLe-1	Version: 1.0	Page 14 of 17

- Arrytmias at same time points as for heart rate >200/minInotropic score > 20 at same time points as for heart rate >200/minThrombocytes < 50 10⁹/L on the first postoperative morning
- Hypokalemia < 3.5 mmol/L at same time points as for heart rate >200/min

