**Table 1 Study Activities**

	Pre-study	Surgery	Post-surgery				Follow-up		
			T0	T1	T2	T3	T4		
At:	Baseline		2 hours	6 hours	24 hours	48 hours	4, 5 days	30 days	
Informed consent	X								
Demography	X								
Weight, height	X								
Medical history	X								
Physical examination	X								
Inclusion/exclusion criteria	X	X							
Randomization		X							
Surgery		X							
Levosimendan/Milrinone		X	X	X	X	X			
Pulse, Blood pressure		X	X	X	X	X	X	X	
Routine laboratory screening (minimum Creatinine, S-K)		X	X	X	X	X	X	X	
Pharmacokinetics					X	X	X	X	
Study specific blood		X	X	X	X	X			
Continuous ECG monitoring		X	X	X	X	X	X		
Continuous hemodynamic and respiratory monitoring		X	X	X	X	X			
Serious Adverse event recording		X	X	X	X	X			
Urine production		X	X	X	X	X		X	
Adverse Events registr*		X	X	X	X	X	X	X	X
Registration of mortality									X
Registration of length of stay (bed-days)									X
Routine echocardiography (preoperative, after CPB termination, first postoperative day, and at discharge)									

\* Registration of adverse events will also be performed at day 30 (e.g. telephone contact with the parents if the patient is at home)

**Figure 2** *Study flow chart*

The infusion of Levosimendan/Milrinone will start perioperatively when the patient is on cardiopulmonary bypass. The infusion will thereafter continue in the intensive care unit (ICU) and will be terminated after 24 hours. Patients in both groups will be followed up according the normal clinical routines. Routine echocardiography will be performed at pre-defined time-points as a clinical routine (pre-operatively, after termination of CPB intra-operatively, at first postoperative day, and at discharge). Extra study specific blood samples will be taken from the included patients. Patients who develop AKI will be identified by increase in s-Creatinine >50% from baseline. The usual clinical and laboratory data will be routinely obtained and recorded in the hospital electronic records. Study-specific parameters will be registered in a CRF.

Follow-up of the patients will continue 4 days after termination of Levosimendan/Milrinone infusion. The follow-up parameters, included in case report form (CRF),

include among others treatment-needling hypotension, treatment-needling arrhythmias, s-Creatinine, s-Potassium and albumin.

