## **6. STUDY CONDUCT AND METHODS**

### **6.1 Start and termination of study infusion and follow-up**

The infusion of Levosimendan/Milrinone starts during CPB and will be continued in our PICU for 24 hours. After 24 hours the infusion rate will be decreased and set to the half infusion rate for 2 hours. If the patient does not tolerate this dose reduction, we will shift from test medication to Milrinone and start a Milrinone infusion. If the patient tolerates the dose reduction for 2 hours, then we will stop completely the infusion of the test medication. Two 2 hours after reducing the infusion rate by 50%, we will stop the infusion completely.

Both groups are followed up according to the normal clinical routines as long as they stay at PICU. Extra blood samples, in addition to those needed for usual clinical care, will be taken from the patients according the specified scheme presented in this document.

The trial follow-up of the patients will continue 4 days after termination of Levosimendan/Milirone infusion. CRF includes the clinical and laboratory follow-up

parameters as well as adverse events (like treatment needing hypotension and arrhythmias), adverse reactions and SUSARS (see section 7).

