### 7.1.4 Adverse reactions of study medication

Data regarding adverse effects of Levosimendanmendan and Milrinone in a pediatric population are scarce. The reported adverse reactions of Levosimendanmendan in adults are hypotension and arrhythmias (both ventricular and supra ventricular). Reported adverse reactons of Milrinone are headache, ventricular tachycardia, supraventricular arrhythmias and hypotension. The reactions are probable to occur in the present study and are treatable. Careful and adequate monitoring will be present

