### **7.1.9 Adverse Events based on examinations and tests**

Deterioration as compared to baseline in protocol-mandated laboratory values, vital signs and other safety variables will only be reported as AEs if they fulfil any of the SAE criteria or are the reason for discontinuation of treatment with the investigational product. If deterioration in a laboratory value/vital sign is associated with clinical signs and symptoms, the sign/symptom will be reported as an AE and the associated laboratory result/vital sign will be considered as additional information. Any new or aggravated clinically relevant abnormal medical finding at a physical examination as compared with the baseline assessment will be reported as an AE.

Clinically relevant deterioration in non-protocol-mandated measurements will be reported as AE(s).

Wherever possible the reporting investigator uses the clinical, rather than the laboratory term (eg, anaemia versus low haemoglobin value).

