**Amendment: Definition of adverse events (AE) in MiLe-1**

**Reason for Amendment:**

Lack of definition of AEs, in contrast to SAEs which were well-defined.

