**Actions to be taken:**

AEs, according to following criteria, for all included patients will separately be registered.

AEs Criteria:

1. Heart rate > 200/min at these time points: 2, 6, 10-12 hours after CPB weaning, first postop morning at 6 o'clock and 24 hours after CPB weaning [1]
2. Arrhythmias (rhythm other than sinusrythm). Same time points as in no 1 [2,3]
3. Inotropic score > 20 at the same time points as in no 1 [4]
4. Thrombocytes < 50.000 on the first postoperative morning [3]
5. Hypokalemia < 3.5 at the same time points as in no 1 [2]

References:

- 1) Advanced Paediatric Life Support (APLS)
- 2) Pharmaceutical Specialities in Sweden (Farmaceutiska Specialiteter i Sverige: Fass)
- 3) Hoffman TM. Cirkulation 2003;107:996-1002
- 4) Gaies MG. Pediatr Crit Care Med 2010; 234-238

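### Hypotension needing treatment, a listed reaction to both study drugs, is missing from the five adverse-event categories in the AE amendment and SAP 4.5.1, so non-serious episodes would probably not be counted by name

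*SAP*

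**What the plan says.** Protocol 7.1.4 gives the reported reactions to levosimendan "in adults are hypotension and arrhythmias (both ventricular and supra ventricular". It adds that the reported reactions to "Milrinone are headache, ventricular tachycardia, supraventricular arrhythmias and hypotension". It regards such reactions as likely in this trial and treatable.

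The protocol twice names treatment-needing hypotension as CRF content. The design text after Table 1 in section 3 says that the follow-up parameters "include among others treatment-needling hypotension, treatment-needling arrhythmias, s-Creatinine, s-Potassium and albumin". Section 6.1 says that the CRF holds the follow-up "parameters as well as adverse events (like treatment needing hypotension and arrhythmias), adverse reactions and SUSARS (see section 7").

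A later amendment on the definition of adverse events gives its reason as "Lack of definition of AEs, in contrast to SAEs which were well-defined". It then states: "AEs, according to following criteria, for all included patients will separately be registered". Five criteria follow: heart rate above 200/min, arrhythmia, inotropic score above 20, platelets below 50 × 10⁹/L and potassium below 3.5 mmol/L. SAP 4.5.1 repeats these five and says that "AEs are collected in the following 5 categories at CRF page Adverse Events". Neither list includes hypotension or any blood-pressure criterion.

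SAP 5.6.1 and Tables 14.5.1 to 14.5.3 summarise any AE, all AEs and treatment-related AEs by arm.

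**The concern.** Both drugs are vasodilators given to infants around bypass, and Protocol 1.9 names a fall in blood pressure as the possible initial haemodynamic adverse effect. The protocol pairs treated hypotension with treated arrhythmia wherever it describes the CRF. The amendment and the SAP keep arrhythmia and leave out hypotension, and neither document gives a reason. SAP section 7, where changes from the protocol would be explained, holds only a template instruction.

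At stake is how the safety comparison reads. A table headed as covering all serious and non-serious AEs, with no hypotension row, could be taken as reassurance when the event was simply not a category. Protocol 1.4 also names renal hypoperfusion as one cause of AKI, so treated hypotension by arm would help a reader interpret the kidney result.

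**Working it through.** The plan states no figure to reproduce on this point. The check is a comparison of texts, followed by two illustrative calculations.

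**1. Named events against the five categories**

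| Event named in Protocol 3 and 6.1 | Reaction listed in 7.1.4 | In amendment and SAP 4.5.1 |
|---|---|---|
| Arrhythmia needing treatment | both drugs | yes (arrhythmia) |
| Hypotension needing treatment | both drugs | no |

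The SAP announces five categories and lists five. Hypotension is in none of them.

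**2. Does another rule bring it in?** Under Protocol 7.1.9, worsening of a protocol-mandated vital sign "will only be reported as AEs if they fulfil any of the SAE criteria or are the reason for discontinuation of treatment" with the study drug. A non-serious fall in pressure that is treated while the infusion continues does not qualify by that route. Serious hypotension does have a route, as an SAE (SAP 4.5.2).

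**3. What other planned data capture**

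- Inotropic score above 20 is itself an AE category, checked at 2, 6 and 10–12 h, at 6 am and at 24 h. It catches heavily supported cases at those times, under another label. Protocol 7.1.15 makes fluid the first step, and fluid does not raise the score.
- Albumin, plasma and red cells are recorded yes/no in the operating room and per ICU day (SAP 4.2.1, 4.2.2), and fluid balance is recorded daily (4.4.3). None carries the reason for giving fluid.
- Mean arterial pressure is read at T0–T4, at 8–12 h and each postoperative morning (SAP 4.4.2, 4.4.3). Kidney NIRS, lactate and central venous saturation are also recorded at set times.
- SAP 8.3 plans no formal listings, so a listing would not show individual episodes.

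**4. Illustration: chance that a scheduled pressure reading falls inside an episode.** There are six readings in the first 24 h after weaning: T1, T2, T3, 8–12 h, 6 am and T4. Assume that an episode of d minutes starts at a uniformly random time in 1,440 min. The simple formula is 6 × d / 1440:

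- d = 5: 30/1440 = 2.1%
- d = 10: 60/1440 = 4.2%
- d = 30: 180/1440 = 12.5%

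Now place the readings at 7.5, 120, 360, 600, 960 and 1440 min (8–12 h taken as 10 h, 6 am as 16 h after weaning). T1 can then catch only episodes that start in the first 7.5 min:

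- d = 5: (6 × 5)/1440 = 2.1%
- d = 10: (7.5 + 5 × 10)/1440 = 4.0%
- d = 30: (7.5 + 5 × 30)/1440 = 10.9%

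The range is therefore about 2% for 5 min, 4% for 10 min and 11–12.5% for 30 min. The durations are assumptions. Protocol Table 3 says only that episodes last minutes, and it describes events due to the disease or the surgery, not drug reactions.

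**5. Precision of an added row.** With 35 per arm and equal incidence p, the 95% half-width for the difference is 1.96 × √(2p(1−p)/35):

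- p = 0.3 or 0.7: 1.96 × √(0.42/35) = 21.5 points
- p = 0.5: 1.96 × √(0.50/35) = 23.4 points

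The row can describe the arms but can exclude only large differences.

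**The case against.** **The SAP follows the amendment.** This is correct. A reader might infer that the SAP departed from the protocol. It did not: the tension lies between the older protocol text and the later amendment, and a fix to the SAP alone would be incomplete.

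**The five criteria may be additional.** The amendment says that they are registered separately, which can mean on top of the general AE definition in Protocol 7.1.6. SAP 5.6.1 does not restrict its rows to the five, and the CRF is not in the documents. This stands as a limit on certainty. A reader might infer that non-serious hypotension is certain to be absent from the AE tables, but the documents support only that this is the likely result of how SAP 4.5.1 is worded.

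**Other data cover much of the ground.** They do in part, as set out above, and blood pressure is certainly not ignored. What is missing is a count of infants and episodes treated for low pressure.

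**Fixed-time sampling is not special to hypotension.** The heart-rate and arrhythmia categories are sampled at the same sparse times. This is fair. The percentages show only that scheduled pressures cannot stand in for an episode count. They are not evidence that hypotension is treated worse than the other categories.

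**Hypotension is background after this surgery, and the yield is low.** Table 3 does call such episodes usual, and precision is poor. But arrhythmia has the same entry and was kept, and comparison by randomised arm is how a drug effect is separated from background.

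**Conclusion.** The gap is real and modest. Treated hypotension is a listed reaction to both drugs and a named CRF item, and the amendment's list, carried into SAP 4.5.1, leaves it out without explanation. If the five categories are what the AE tables draw on, non-serious treated hypotension would not be counted under its own name in Tables 14.5.1 to 14.5.3, and the other planned data replace that count only in part.

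This conclusion rests on reading the SAP's statement about collection at face value, without sight of the CRF. The detection percentages are illustrations under assumed durations and a random start.

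A reader might go further and infer that the omission biases the AKI comparison. The documents support no such claim in either direction: hypotension reporting does not enter the primary analysis. Correcting the list is an inexpensive improvement to safety reporting.

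**What to change.** Add a sixth category, hypotension needing treatment, to both the amendment's AE list and SAP 4.5.1. Define it by the steps in Protocol 7.1.15: fluid given, or a vasoactive drug started or increased, for low blood pressure. Take it from the CRF item named in Protocol sections 3 and 6.1.

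Report infants with at least one episode, and the number of episodes, by arm in the safety population. Label the result descriptive. Show *Any AE* with and without this category, because a usual event could push that row close to 100% in both arms.

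If the final CRF lacks the item, state in the report that non-serious hypotension was not collected as an AE.

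The cost is a change to two documents and an added row in the AE tables. If the CRF holds the item as the protocol says, no new data collection is needed, and treatment and blinding are untouched. The downsides are a high background rate, some judgement about why fluid or a vasoactive drug was given, and the wide intervals shown above.
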